7.5 Analyses of the Secondary Outcome Measures

The secondary (efficacy) outcome will be analyzed in the ITT population (defined in Section 3.1.3) with a generalized linear mixed model approach to adjust for correlation between UDS from the same participants and to provide conditional interpretation of the treatment effect. The model will include fixed effects for treatment, major depressive episode (MDE), week, and site and a random effect for participant. It is important to note that a repeated measure, binary response of negative UDS, for each UDS provided by each participant, will be used as the outcome, as opposed to the total percentage of negative UDS. The model used still allows inference on the overall probability of a negative weekly UDS during the treatment period. Additionally, week will enter the model as a categorical variable to allow greater flexibility on the effect of week. Section 7.9 describes missing data handling procedures for the secondary outcome sensitivity analyses.

The assessment of the significance of the treatment will be done by testing the significance of the treatment parameter at the 0.05 significance level. The treatment effect will be measured by an odds ratio with an associated 95% confidence interval. The corresponding SAS code is provided below:

```
proc glimmix data = data method = quad;
  class site week participant;
  model y(event = '1') = trt mde week site / dist = binary link
    = logit solution;
  random intercept / subject = participant;
run;
```

where:

- data is a dataset with one row per weekly UDS per participant for the specified primary substance of use,
- y is the binary variable with a value of 1 indicating the UDS for that participant was negative and 0 indicating positive UDS result,
- trt is a binary variable with a value of 1 indicating active rTMS and 0 indicating sham rTMS,
- mde is a binary variable with a value of 1 indicating the presence of MDE,
- week is the study week (1 – 8, categorical), and
- site is a categorical variable containing which of the sites each participant was enrolled in.

In the event that the estimate of the variance component related to the within participant correlation (i.e., the ICC for UDS) is so close to 0 that it causes the overall covariance matrix to not be positive definite, the model will be refit without the random effect for the correlation within participant. This is accomplished simply by removing the random effect.

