Participants who dropped out may have had different patterns of substance use after dropout than those who remained in the study. The values for missing UDS after dropout might not retain the trend of prior observations since the participant was no longer exposed to the study environment. In fact, substance use patterns after dropout for a participant in the active rTMS treatment arm may more closely resemble participants in the sham treatment arm than other active rTMS participants.

Separate analyses will be performed for CUD and MUD as described for the main analysis of the secondary outcome measure in Section 7.4.

In the first step of imputation, a Markov Chain Monte Carlo (MCMC) method will be used to impute the values of missing outcomes from intermittent missingness under the assumption of MAR. The SAS code for imputing missing data from intermittent missingness is given below. Note the categorical variables (e.g., site, strata) must be in the dataset as dummy variables for MCMC imputation.

```
proc mi data = secondout_wide out = imp1
    minimum = 0 maximum = 1 round = 1
    n impute = 50 seed = 123;
    by trt;
    mcmc impute = monotone chains = multiple;
    var site1 site2 site3 mde week1-week8;
run;
```

where *secondout_wide* is the wide form of the secondary outcome dataset with one observation per participant; *imp1* is the output dataset of monotone missingness; *minimum*, *maximum*, and *round* restrict the imputed values to possible UDS values (negative and positive); *trt* is treatment arm ('rTMS', 'Sham'); *mde* is the major depressive episode (MDE) stratification value, and *week1-week8* provide the UDS values for Week 1 – Week 8, respectively. The analysis method for imputation will follow that used for the secondary outcome analysis. This step provides 50 imputed datasets with monotone missingness by filling in the missing values from intermittent missingness with the statement "impute = monotone." The missing values due to intermittent missingness are imputed assuming that the intervention effect is still carried out while the participants remain in the study.

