Using the monotone missingness dataset created in the first step, the second step imputes missing values from dropouts under the assumption of MNAR. This process of control-based pattern imputation assumes that after dropout the unobserved values in the active rTMS arm followed the path of the observed values in the sham arm. Based on this assumption, only the observed values in the sham arm are used to derive the posterior distribution of the parameters from which the missing values in both active rTMS and sham arms are imputed. This approach is conservative as it tended to reduce the difference between active rTMS and sham. The SAS code for imputing missing data from dropout is below.

```
proc mi data = imp1 out = imp2
    minimum = . . . 0 0 0 0
    maximum = . . . 1 1 1 1
    round = . . . 1 1 1 1
```

```
nimpute = 1 seed = 123;
class trt site mde;
var site mde week1 week2 week3 week4 week5 week6 week7 week8;
monotone reg;
mnar model(week1 week2 week3 week4 week5 week6 week7 week8/
modelobs=(trt=Sham));
run;
```

where *site* is the participant's site, *mde* is the major depressive episode (MDE) stratification value, and the remaining variables and proc mi options were as described above. The *monotone reg* statement specifies a regression imputation method for monotone missingness and *mnar* imputed missing values under the MNAR assumption for variables week1-week8. The *modelobs* statement specifies that only observations where *trt* = Sham are used to derive the imputation model following the control-based pattern imputation method.

After the complete datasets are generated, the dataset is transposed into long form by week and analyses of the imputed datasets using the standard procedure for generalized linear mixed effect model are performed separately for each imputed dataset using the *by_imputation_* statement.

```
proc glimmix data = imp_long method = quad;
  by _imputation_;
  class trt (ref = 'Sham') site week mde patid;
  model y(event = '1') = trt mde week site /
    dist = binary link = logit solution;
  random intercept / subject = patid;
  estimate "rTMS vs Sham" trt 1 -1 / cl e ilink exp;
  ods output estimates = est_imp;
run;
```

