7.10.2 Missing Data Analysis

The analysis method for imputation will follow that used for the secondary outcome analysis. If the full original model does not produce reliable results, the simplified model with a fixed effect for treatment arm and a random effect for participant will be used. If the simplified model does not converge or produce reliable results, summary statistics will be reported.

Multiple imputation results may not be reported if the planned imputation algorithms fail due to lack of variability in the observed data.

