10.2 Power Analysis

Similarly, power analysis via simulation studies was conducted for the secondary (efficacy) outcome. Since participants enrolled with cocaine use disorder and participants enrolled with methamphetamine use disorder are analyzed separately, a sample size of 80 is used. Participants randomly assigned to receive the sham rTMS had their number of negative UDS generated from a binomial distribution with $n = 8$ and $p = 0.36$. The probability of 0.36 for a negative UDS was based on the results found in Terraneo et al. (2016) when comparing rTMS to control on cocaine use. They found, at baseline, an average of about 4.5 use days per week. This would mean then that there is roughly $4.5/7 = 0.64$ probability of use on any given day and thus about 0.36 probability of no use on any given day. Although the UDS look-back period may be roughly 3 days, so that to be truly negative a participant would have to be not using for past 3 days, which may mean that true probability of negative UDS may be less than 0.36, a proportion further from 0.5 (holding all else constant) would generally result in higher power. Therefore, the use 0.36 is conservative in this sense. Regardless, different values were considered as well to gauge the sensitivity of the results to this assumption of 0.36. This same base probability, p , in the sham group is used for methamphetamine as well because no results on methamphetamine use when studying rTMS have been found. Participants randomly assigned to real rTMS had their number of negative UDS generated from a binomial distribution with $n = 8$ as well, but with p varying based on the effect sized used. In the same paper by Terraneo et al. (2016), they found roughly a 6.5 odds ratio (OR) for any use. The power analyses performed here considers a few lower, more conservative, odds ratio levels of 2, 3, 4, and 5. This includes the clinically meaningful odds ratio of 2. In order to match the model to be fit and to allow correlation between UDS from the same participant, a random effect from a normal distribution was added to the logit of the probability value used to generate the number of negative UDS for each participant, with fixed standard deviation. The standard deviation used was determined based on a small set of possible within-participant correlation, or intraclass correlation (ICC), values. Specifically, ICCs of 0.25 and 0.5

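### The fourth missing-data method imputes yes/no urine results with rounded normal models, which distorts the imputed negative rate in a direction that depends on the true rate; logistic imputation with a sparse-data provision should replace it (minor).

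*SAP*

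**What the plan says.** SAP 7.5 codes the outcome as binary, with a "value of 1 indicating the UDS for that participant was negative and 0 indicating positive UDS result". The main analysis is a logistic mixed model on the observed weekly results, without imputation.

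SAP 7.9 adds four missing-data sensitivity analyses. The fourth is multiple imputation in two steps:

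- **Step 1, intermittent gaps.** "a Markov Chain Monte Carlo (MCMC) method will be used to impute the values of missing outcomes from intermittent missingness", run separately by arm on the eight weekly 0/1 values. The code sets "minimum = 0 maximum = 1 round = 1", and the text says that these options "restrict the imputed values to possible UDS values (negative and positive").
- **Step 2, dropout.** The monotone reg "statement specifies a regression imputation method for monotone missingness". Parameters come from the sham arm only and are used for dropouts in both arms. Weekly values are again bounded and rounded.

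The completed data go into the logistic mixed model and are pooled. No logistic or discriminant option is named in either step. The SAP describes the control-based step as conservative because it tends to narrow the difference between arms.

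SAP 7.10.2, added after database lock, says: "Multiple imputation results may not be reported if the planned imputation algorithms fail due to lack of variability in the observed data".

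**The concern.** Both steps draw from a normal distribution for a variable that can only be 0 or 1, and then force the draw to 0 or 1. The share of draws that become 1 is the normal area beyond 0.5, which is generally not the probability that the model was fitted to. The imputation model also does not match the logistic model used afterwards.

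Method four is the only planned analysis with an explicit control-based missing-not-at-random model for dropout, and the SAP's table shell for the sensitivity analyses (Table 60) sets it beside the main result. If rounding moves the imputed rates, a gap between the two rows would be read as sensitivity to dropout. SAP 7.10.2 does not catch this, because it covers only algorithms that fail. A rounded normal imputation can run to completion and return biased values.

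**Working it through.** **Inputs.** Sham rate: "The probability of 0.36 for a negative UDS was based on the results found in" a cited pilot study (SAP 10.2), with 0.26 and 0.46 also considered. Effects: "lower, more conservative, odds ratio levels of 2, 3, 4, and 5". At a sham rate of 0.36 these give active-arm rates of 0.529, 0.628, 0.692 and 0.738. ICC is 0.25 or 0.5. N is 80 per use disorder, with 8 weekly results each. The proportion missing is not given.

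**Reproducing the plan's own figures.** The documents print no figure for the imputation, so the data model was checked against the power table (SAP Table 3). The random-effect SD is √[ICC/(1−ICC) × π²/3] = 1.047 and 1.814, against about 1.05 and 1.81 in the SAP. Simulated power (treatment term only, 2,500 runs, N = 80, sham 0.36):

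| ICC | OR | SAP | Simulated |
|---|---|---|---|
| 0.5 | 4 | 86% | 84.8% |
| 0.25 | 2 | 67% | 66.6% |
| 0.5 | 2 | 35% | 34.0% |

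**Closed form.** Draw from Normal(p, s²) with s = √[p(1−p)], and let F(t) = Φ((t−p)/s). The SAP does not state how bounding and rounding interact, so three readings are shown:

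- A, round at 0.5: 1 − F(0.5)
- B, round, and redraw unless 0 or 1: [F(1.5) − F(0.5)] / [F(1.5) − F(−0.5)]
- C, redraw until within 0-1, then round: [F(1) − F(0.5)] / [F(1) − F(0)]

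Example at p = 0.36: s = 0.48 and (0.5 − 0.36)/0.48 = 0.292, so A gives 1 − Φ(0.292) = 0.385.

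| True p | A | B | C |
|---|---|---|---|
| 0.05 | 0.019 | 0.020 | 0.033 |
| 0.075 | 0.053 | 0.054 | 0.087 |
| 0.15 | 0.163 | 0.169 | 0.237 |
| 0.26 | 0.292 | 0.303 | 0.364 |
| 0.36 | 0.385 | 0.394 | 0.431 |
| 0.46 | 0.468 | 0.471 | 0.482 |
| 0.53 | 0.524 | 0.522 | 0.514 |
| 0.69 | 0.659 | 0.649 | 0.599 |
| 0.74 | 0.708 | 0.697 | 0.636 |

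The bias changes from downward to upward at p = 0.118 (A), 0.112 (B) and 0.066 (C), and back to downward at 0.5. By symmetry it turns once more close to 1, beyond the planning rates.

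**One missing week imputed from the other seven** (40,000 simulated people):

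| True rate | Rounded, A to C | Logistic |
|---|---|---|
| 0.298 | 0.329-0.385 | 0.298 |
| 0.384 | 0.407-0.437 | 0.382 |
| 0.409 | 0.422-0.443 | 0.411 |
| 0.657 | 0.586-0.631 | 0.657 |
| 0.052 | 0.022-0.037 | 0.050 |
| 0.078 | 0.057-0.094 | 0.076 |

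**Step 2 with dropout** (40,000 per arm; sham-based sequential imputation). Assumed dropout is 35% if Week 1 is positive and 20% if negative, with the first missing week between 2 and 5. Results are given as A then C.

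- Median sham rate 0.26, ICC 0.25, sham arm: true 28.1%; imputed 31.8% or 38.8%; logistic 27.9%. The largest shift is 38.8 − 28.1 = 10.7 points. Active arm: 35.3% or 41.1%, against 31.5% with logistic imputation.
- Median sham rate 0.36, ICC 0.5, sham arm, over repeat runs: true 36%; imputed 39-40% or 43-44%; logistic 36-37%.

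Because step 2 uses sham parameters for both arms, the shift at these rates is upward in both arms.

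Completed-data odds ratios, with ranges over repeat runs:

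| Median sham rate | A | C | Logistic |
|---|---|---|---|
| 0.09 (ICC 0.25) | 2.22 | 2.08 | 2.25 |
| 0.07 (near-zero correlation, true OR 2) | 1.81-1.83 | 1.73-1.74 | 1.76-1.77 |
| 0.05 (near-zero correlation, true OR 2) | 1.86-1.88 | 1.82 | 1.75-1.77 |

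The largest fall is 2.08/2.25 = 0.924, or −8%. The largest rise is 1.86/1.75 = 1.063, or +6%.

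**Which rate applies?** The observed sham rate is not printed. SAP Table 7 (n = 52, OR 2) gives 40/53/63% power at the observed rate −0.025, 0 and +0.025. Take independent results, 26 × 8 = 208 per arm, and variance 1/(208·p₀q₀) + 1/(208·p₁q₁), where q = 1 − p. At p₀ = 0.07, p₁ = 0.131 and SE = 0.341, so power is Φ(0.693/0.341 − 1.96) = 53%. At 0.045 and 0.095 it is 38% and 64%. Table 7 therefore suggests about 0.07-0.08, and Table 5 about 0.05-0.06, where the direction is downward or mixed.

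**Can a logistic model be fitted there?** With 26 per arm, the chance that a given week has no negative result is 0.95²⁶ = 0.264 at a rate of 0.05 and 0.925²⁶ = 0.132 at 0.075. Taking weeks as independent, the chance for at least one of 8 weeks is 1 − (1 − 0.264)⁸ = 91% and 1 − (1 − 0.132)⁸ = 68%.

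**The case against.** The strongest reply is that little depends on this. It is one of four missing-data sensitivity analyses of a secondary outcome, in a pilot that the SAP says is not powered for efficacy. The odds ratio moves by single-digit percentages, under an assumed dropout rate and an unstated order of bounding and rounding. All of that stands, and it sets the priority.

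Several stronger readings are tempting, and the documents do not support them.

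- *Rounding always adds false negatives, most of all at low rates, and so shrinks the odds ratio.* The direction reverses above 0.5 and at very low rates. Near 0.05-0.07, plain rounding raised the odds ratio.
- *The reported lack of variability shows that negative results were rare.* SAP 7.10 does not say which boundary was reached. The example in 7.10.1 is a subgroup with no positive results. The low rate above is inferred from power figures and assumes almost no within-person correlation.
- *This is the only analysis that departs from missing at random.* Imputing all missing results as negative, and separately as positive, also departs from it and brackets the extremes without a normal model. What is particular to method four is the explicit control-based dropout model.
- *Plain logistic imputation settles it.* In sparse weeks it would often separate.

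SAP 7.10.2 allows non-reporting if the algorithms fail. That is a reasonable provision, but it does not address an algorithm that runs and is biased.

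**Conclusion.** The point holds in a limited form. Bounded and rounded normal imputation does not preserve the probability of a negative urine result. Imputed rates are too high across the sham planning range, too low at the planned active-arm rates above 0.5 where step 1 imputes by arm, and too low or mixed near 0.05-0.08. The shifts reach about 11 points in an imputed rate and about 1-8% in the completed-data odds ratio, either way. The claim that the method is conservative is therefore not assured.

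The finding that rounding distorts the rates needs only the method as written. The sizes rest on large-sample simulation, the SAP's random-intercept model, about 30% dropout and the three readings of the options. As reproduced, the step 2 option lists also show 7 entries for 10 variables. That may be a loss in text extraction, and nothing here depends on it. Priority is minor.

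**What to change.** In SAP 7.9, fourth method:

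1. Replace step 1 with fully conditional specification, by arm, using logistic models for week1-week8 declared as classification variables. Step 1 should still fill only intermittent gaps, so any value drawn after dropout is set back to missing before step 2.
2. Replace monotone reg in step 2 with MONOTONE LOGISTIC under the same sham-based MNAR MODELOBS rule.
3. Drop MINIMUM, MAXIMUM and ROUND in both steps.
4. Specify an augmented or penalised likelihood, with merging of sparse weeks as the fallback. Keep the 7.10.2 provision for the case where this also fails.

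The cost is a few lines of SAS and SAP text, plus some loss of week-level detail if weeks are merged. Because the database is already locked, the change should be dated and labelled as post-lock, as SAP 7.10 does for its own changes. If the method is left as it is, the report should say that the imputation used rounded normal models, and a difference from the main result should not be attributed to dropout alone.

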To draw statistical inference based on the results from the imputations, the combination rules are applied in MIANALYZE procedure (Little and Rubin, 2002; van Buuren, 2007). Proc MIANALYZE is set to estimate the pooled variance from two components: within-imputation variance and between-imputation variance. Within-imputation variance is the average of the mean of the within variance estimate in each imputed dataset. Between-imputation variance reflects the extra variance due to the missing data, which is estimated by taking the variance of parameter of interest estimated over imputed datasets.

```
proc mianalyze data = est_imp;
  modeleffects estimate;
  stderr stderr;
  ods output parameterestimates = est_pooled;
run;
```

The pooled results are then exponentiated to calculate the odds ratio and 95% confidence limits.

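### Control-based multiple imputation, step 2: the printed PROC MI code has no BY _Imputation_ statement and supplies 0/1 limits for only four of the eight weekly outcomes

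*SAP*

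**What the plan says.** SAP 7.9 gives four ways of handling missing weekly urine drug screen (UDS) results. The fourth is a two-step multiple imputation, run separately for the cocaine and methamphetamine groups.

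- **Step 1** fills intermittent gaps within each arm. The text says: "This step provides 50 imputed datasets with monotone missingness". It explains that the minimum, maximum and round options "restrict the imputed values to possible UDS values (negative and positive").
- **Step 2** fills the weeks after dropout, in both arms, from a model built on sham observations only. The listing opens "proc mi data = imp1 out = imp2", sets "nimpute = 1 seed = 123", and names its variables as "var site mde week1 week2 week3 week4 week5 week6 week7 week8". Each of the three limit lists holds three blank entries followed by four values. No BY statement appears before the step ends. The text below the listing says that "the remaining variables and proc mi options were as described above".
- **Analysis and pooling.** The mixed models "are performed separately for each imputed dataset", using a BY statement on the imputation index, and PROC MIANALYZE pools them. On the pooled variance the SAP says: "Between-imputation variance reflects the extra variance due to the missing data".

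**The concern.** The text and the step-2 listing describe different procedures, in two respects.

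**(a) No BY statement.** One imputation per call fits the text only if the call is repeated within each of the 50 data sets from step 1. The authors print BY where they want it elsewhere: by arm in step 1 and by imputation in GLIMMIX. Without it, step 2 fits one sham model, with one draw of its parameters, to all 50 stacked copies of each participant.

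**(b) Short limit lists.** Eight weekly outcomes need 0/1 limits, and each list supplies four values. Step 2 uses linear regression imputation, which draws continuous values, and the next model is declared binary. Any week left without limits could therefore pass non-binary values to GLIMMIX, or the step could stop.

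At stake is the multiple-imputation row of SAP Table 60. It is the only one of the four methods that treats dropout as missing not at random by reference to the sham arm. Run as printed, that row would not come from the stated procedure. There is also a reporting risk. SAP 7.10.2 lets this result go unreported if the algorithm fails for lack of variability in the data, and a stop caused by faulty option lists could be mistaken for that.

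**Working it through.** **1. The SAP's own figure.** Step 1 requests 50 imputations in each arm, which gives 50 labelled data sets, as stated. With a BY statement, step 2 gives 50 × 1 = 50 completed data sets, as GLIMMIX and MIANALYZE require. Step 2 as printed has no BY statement.

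**2. Count of the step-2 lists.**

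| Item | Entries |
|---|---|
| VAR (site, mde, week1–week8) | 10 |
| minimum | 7 (3 blank, 4 zeros) |
| maximum | 7 (3 blank, 4 ones) |
| round | 7 (3 blank, 4 ones) |

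Matched by position, the blanks fall on site, mde and week1, and the four values fall on week2–week5. Week6–week8 have no entry. Week1 matters only for a participant with no UDS at all, because any other gap at week1 is filled in step 1.

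**3. Share of outcome cells in weeks 6–8, under positional matching only.** If the last UDS is in week k (k = 1 to 7), 8 − k weeks are imputed:

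- Imputed weeks: 7, 6, 5, 4, 3, 2, 1 (total 28).
- Of these, in weeks 6–8: 3, 3, 3, 3, 3, 2, 1 (total 18).
- With dropout even over the seven weeks: 18/7 = 2.57 cells per dropout.

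Take n = 52, the cocaine-group count in SAP 11.1.1, which gives 52 × 8 = 416 person-weeks. The dropout rates are assumed:

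| Dropout | Participants | Cells in weeks 6–8 | Share of 416 |
|---|---|---|---|
| 20% | 10.4 | 26.7 | 6% |
| 40% | 20.8 | 53.5 | 13% |
| 60% | 31.2 | 80.2 | 19% |

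These are shares of outcome cells, not bias in the odds ratio. In a separate simulation (n = 80, P(negative) 0.36, random-effect SD 1.05), every imputed value in weeks 6–8 was non-binary when those weeks had neither limits nor rounding. About 9–10% of the regression draws would round to a value outside 0/1 unless bounded.

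**4. Effect of the missing BY, by simulation.** Assumptions:

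- 40% dropout spread evenly after weeks 1–7, with no intermittent gaps and no site or MDE terms.
- True odds ratio 1, sham negative rate 10% or 36%, and the SAP's random-effect SDs of 1.05 and 1.81.
- Sham-only sequential regression on prior weeks, with draws rounded to 0/1 in all weeks.
- 50 imputations with labels kept.
- Marginal log odds ratio with participant-clustered standard error, 400 trials per cell.

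| Median, no BY against BY | n = 52 | n = 80 |
|---|---|---|
| Pooled SE ratio | 1.014–1.023 | 1.011–1.017 |
| Between-imputation variance ratio | 0.61–0.97 | 0.73–0.99 |
| Odds ratio factor | 1.018–1.049 | 1.013–1.030 |

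At n = 52 the 90th percentile of the odds ratio factor was 1.05–1.14. The pooled SE rises although between-imputation variance falls, because within-imputation variance rises by 3–7%.

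**The case against.** The strongest reply is that the method is stated correctly and only a listing is wrong. An analyst who follows the prose reaches the intended procedure, and the executed program may already do so. That is fair. It makes this a correction of code and leaves the method as it is. It does not remove the mismatch, because SAP Section 14 records that detail was added to 7.9 in version 2.0 to clarify the approach, and this code is part of that specification.

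Second, the numerical effect of (a) is close to noise. In a smaller simulation (40 trials per cell), two correct BY runs that differed only in seed gave median odds ratio factors of 1.008–1.017 at n = 52 and 1.011–1.020 at n = 80. No BY against BY gave 1.015–1.045 and 1.014–1.025. The shift was about 0.05–0.11 of one pooled SE. So part of the odds ratio factor is Monte Carlo variation, and precision is not overstated in these cells. The between-imputation variance ratio also depends on the set-up: a run at n = 80 with other dropout patterns gave 0.94–1.01. This stands.

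Third, how PROC MI treats short lists, and whether the imputation labels survive step 2, cannot be settled from the documents. This also stands, and only the counts are certain.

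Fourth, the row may never be reported. SAP 7.10 says that the planned models could not be completed, and 7.10.2 allows multiple imputation to be dropped. That limits the consequence but does not make the code right.

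Loss in PDF extraction is unlikely. All three lists show the same seven entries. The break in the listing falls inside the PROC MI statement, before its semicolon, where a BY statement cannot stand.

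**Conclusion.** The concern holds and is minor. The listing lacks the BY statement that the text requires, and its 7-entry lists cannot limit all eight weekly outcomes under any reading. Both facts are direct counts and carry high confidence.

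The consequences are less certain. If labels are kept and all weeks are 0/1, the missing BY raises the pooled SE by 1–2% and moves the odds ratio by a few per cent, partly seed noise. If labels are not kept, the 50 separate fits and their pooling cannot be carried out as described. For the short lists, the 6%, 13% and 19% cell shares apply only under positional matching and the assumed dropout.

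The scope is the fourth of four missing-data sensitivity analyses of a secondary outcome. The primary feasibility outcome, the main secondary model and the other three imputation methods are unaffected.

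**What to change.** In SAP 7.9, step 2:

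1. Sort imp1 by `_Imputation_` (step 1 runs by arm, so its output is grouped by arm) and add `by _imputation_;`.
2. Give each list 10 entries, two blanks for site and mde and then eight values:
   - `minimum = . . 0 0 0 0 0 0 0 0`
   - `maximum = . . 1 1 1 1 1 1 1 1`
   - `round = . . 1 1 1 1 1 1 1 1`
3. Before GLIMMIX and MIANALYZE, confirm that there are 50 labelled data sets and that every outcome is 0 or 1.

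If the executed program already does this, correct the SAP listing and say so. If it ran as printed, rerun the step and replace the multiple-imputation row of Table 60.

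The cost is one PROC SORT, one BY statement, three corrected lists and one data check, with no change to the described method. Monotone logistic imputation would be an optional alternative but is not needed. It may meet separation, given the low variability reported in SAP 7.10.
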